13.3.9 Safety

13.3.9.1 Extent of exposure

A summary of exposure to study drug, by treatment group, including the number of infusions, the total exposure (units/kg) and the duration of exposure (days), will be provided.

13.3.9.2 Adverse events

AEs will be coded according to MedDRA.

TEAEs (events which were not present at baseline or worsened in severity following the start of treatment) will be presented. AEs occurring prior to the start of treatment will be listed only.

The following summaries will be provided:

- A summary of the number and percentage of patients reporting any TEAE, death, at least one severe TEAE, at least one serious TEAE, at least one TEAE possibly related to study drug, at least one TEAE leading to withdrawal from study drug, at least one infusion reaction (as defined in [Appendix C](#)), at least one hypersensitivity reaction by treatment group
- A summary of the number and percentage of patients reporting a TEAE by treatment group, system organ class (SOC) and preferred term
- A summary of the number and percentage of patients reporting a TEAE by treatment group and preferred term
- A summary of the number and percentage of patients reporting a TEAE by treatment group, intensity, SOC and preferred term. For each patient and each TEAE, the maximum reported intensity recorded will be attributed and used in the by-intensity summaries
- A summary of the number and percentage of patients reporting a TEAE by treatment group, by relationship to study drug, SOC and preferred term. The worst

relationship to study drug (most related to treatment) will be attributed and used in the by-relationship summaries

- A summary of the number and percentage of patients reporting an infusion reaction by treatment group, SOC and preferred term
- A summary of the number and percentage of patients reporting hypersensitivity reactions by treatment group, SOC and preferred term.

The following by-patient listing will be provided:

- A listing of all AEs (including non-treatment-emergent events), by treatment group and including centre, patient identifier, AE (SOC, preferred term, reported term), date of onset, date of resolution, duration, severity, seriousness, action taken, outcome and relationship to study treatment.

13.3.9.3 Deaths, serious adverse events, adverse events leading to withdrawal, and other significant adverse events

The following summaries will be provided:

- A summary of the number and percentage of patients reporting a serious TEAE by treatment group, SOC and preferred term.
- A summary of the number and percentage of patients reporting a TEAE leading to withdrawal from study treatment by treatment group, SOC and preferred term.
- A summary of the number and percentage of patients with a SAE outcome of death by treatment group and preferred term.
- A summary of the number and percentage of patients reporting any treatment-emergent OAE by treatment group, SOC and preferred term.
- A summary of the number and percentage of patients reporting any infection by treatment group, SOC, preferred term and category (healthcare-associated, community-acquired).

The following by-patient listings will be presented, each of which will follow the format described for AEs in Section [13.3.9.2](#).

- A by-patient listing of all SAEs.
- A by-patient listing of all OAEs.
- A by-patient listing of all deaths that occurred during the study.
- A by-patient listing of all AEs leading to withdrawal from study treatment.

13.3.9.4 Laboratory evaluation

All laboratory data will be converted from the recorded units to the SI units for presentation. A project reference range will be used for the assessment of out of range parameters.

Summary statistics (mean, median, SD, minimum, and maximum) of the raw data and change from baseline to each scheduled study assessment will be presented for all continuous laboratory parameters. Graphical representations and shift tables of the laboratory data will also be produced.

For categorical urinalysis parameters, shift tables of the number and percentage of patients by classification at baseline and each post-baseline visit will be presented.

13.3.9.5 Vital signs evaluation

Summary statistics (mean, median, SD, minimum, and maximum) of the raw data and change from baseline to each scheduled study assessment for systolic BP, diastolic BP, mean arterial pressure, PR, RR, blood oxygen-haemoglobin saturation and body temperature will be presented by treatment group.

13.3.9.6 Electrocardiogram evaluation

Summary statistics (mean, median, SD, minimum, and maximum) of the raw data and change from baseline to each scheduled study assessment for all ECG parameters will be presented by treatment group.

A shift table from baseline to maximum post-baseline ECG result of the number and percentage of patients with normal/abnormal results as determined by eRT expert assessment will be presented.

The number and percentage of patients meeting threshold criteria for QTcF and QTcB will be presented by treatment group. The threshold criteria for QTcF and QTcB are as follows ([ICH E14](#)):

>450 msec, >480 msec, >500 msec, and increases from baseline of >30 msec and >60 msec.

Plots of corrected QT versus serum concentration of AZD9773 will be presented.

13.4 Determination of sample size

The sample size has been based on the primary outcome variable of VFDs over 28 days. The Phase IIb study in 81 patients with D-CytoFab has been used as an estimate of the between-patient SD (11.380). Assuming this SD holds for the current study, then 100 patients per group will provide 90% power to detect an underlying true difference in means between a dose of AZD9773 and placebo of 4.2 days using a 10% one-sided significance level.

Given this is an exploratory Phase II study, a 10% one-sided significance level is considered appropriate as this implies a 1 in 10 chance of a false positive finding which is consistent with the aim in Phase II of identifying a promising therapy.

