4.2 Rationale for study design, doses and control groups

In a Phase IIb study conducted with D-CytoFab employing a loading dose of 250 units/kg followed by 9 doses of 50 units/kg every 12 hours, there was a significant, prompt and sustained suppression of plasma TNF α during treatment such that TNF α was undetectable in nearly all plasma samples obtained during the entire 5 days of active treatment. Modest and transient rises of TNF α in the treated group occurred in only 2 patients. These 2 patients had the highest baseline TNF α levels of the group, suggesting that dosing was in the optimal region. This dosing regimen was found to significantly improve clinical outcomes for the D-CytoFab-treated group with no adverse safety findings.

In a recently completed Phase IIa study (D0620C00004) conducted with AZD9773, similar effects on plasma TNF α were seen. This particular study was not powered to detect efficacy, but did demonstrate that loading doses of up to 750 units/kg and maintenance doses of up to 250 units/kg every 12 hours were well tolerated in patients with severe sepsis.

In this Phase IIb study, which is powered to detect an effect on the parameter of VFD as a measure of efficacy, both the 250/50 units/kg regimen and the 500/100 units/kg regimen will be evaluated to determine which dose regimen should be employed in further clinical studies to evaluate an effect of AZD9773 on 28-day mortality. Both of these dose regimens were well tolerated in the Phase IIa (D0620C00004) study and the 250 units/kg dose was also well tolerated in the earlier D-CytoFab study. A dose regimen lower than 250/50 units/kg was not included in this Phase IIb study because 250/50 units/kg produced significant clinical benefit with D-CytoFab and there is currently no tolerability concern with the doses chosen for this study. The higher dose will explore the possibility of increased benefit with more TNF α suppression and help define the therapeutic dose-response.

The optimal duration of therapy with an anti-TNF α agent is a balance between intervening to suppress TNF α bursts while not inhibiting the host inflammatory response for too long. A treatment period of 5 days was chosen for the Phase IIb study of D-CytoFab and for the recently completed Phase IIa study (D0620C00004) conducted with AZD9773. In this Phase IIb study the maximum treatment period will also be 5 days.

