6.2.1 Procedures for randomisation

Patients will be randomised to treatment following verification of conformance with eligibility criteria at screening. Central randomisation via IVRS will be used to allocate patients to treatment groups (AZD9773: dose 1, dose 2, placebo) in a 1:1:1 ratio and avoid selection bias.

Randomisation will be performed in blocks based on a computer-generated randomisation scheme provided by AstraZeneca. The size of randomisation blocks will not be disclosed to the study centres. Randomisation will not be stratified. The randomisation scheme will randomly assign the study drug to the randomisation numbers.

Randomisation codes will be assigned strictly sequentially as patients become eligible for randomisation. Randomised patients who terminate their study participation for any reason, regardless of whether the study drug was taken or not, will retain their randomisation number. The next patient will be given the next randomisation number.

Patients who are withdrawn after randomisation will not be replaced.

Sections [6.3.1](#) and [6.3.2](#) describes procedures for blinding and breaking the blind.

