13. STATISTICAL METHODS AND SAMPLE SIZE DETERMINATION BY ASTRAZENECA

13.1 General principles

A comprehensive SAP will be finalised before the last patient visit. All statistical analyses will be performed by PAREXEL. Any deviations from those analyses presented here and/or in the SAP will be detailed in the clinical study report. All outputs will be produced using SAS[®] version 9 or later in accordance with AstraZeneca standards.

All study data will be analysed after the 28-day follow up is complete for all patients. A further analysis will be performed using the Day 90 assessment to understand longer-term patient outcomes (survival and HRQoL).

The following efficacy endpoints will be subject to formal statistical analysis: VFDs, 7-day mortality, 28-day mortality, mortality at Day 90, organ failure-free days, shock-free days and ICU-free days. All other data will only be summarised.

All efficacy data will be summarised and analysed using the per protocol (PP) population. Additionally, an ITT analysis of the endpoints listed above for formal analysis will also be undertaken using the ITT population.

For each of the endpoints subject to statistical analysis the following statistical comparisons will be performed: AZD9773 dose 1 versus placebo, AZD9773 dose 2 versus placebo, and combined AZD9773 dose arms 1 and 2 versus placebo. Although there are three primary comparisons, this is an exploratory Phase IIb study and consequently no adjustment for multiple comparisons will be made.

Unless stated below, no imputation of missing data will be performed. All data recorded on the database will be included in data listings. Any spurious or erroneous data will be queried and followed up until satisfactorily resolved.

The nominal significance level used for this study will be 10% one-sided. However, it is important to note that the study has only been sized based on VFDs over 28 days; this study is not powered to detect a statistically significant difference in 7-day mortality, 28-day mortality or mortality at Day 90. In this case the confidence intervals (CIs) will provide a guide to the possible range of the true treatment effect. This may also be the case for the other secondary endpoints.

Demography data will be summarised using the PP and ITT populations and safety data will be summarised using the safety population. For all summaries of change from baseline, baseline is defined as the latest non-missing assessment prior to first study drug infusion.

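### The 1-in-10 false positive rate given for the 10% one-sided level is per comparison; across the three unadjusted primary comparisons it is about 17%

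*Protocol*

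**What the plan says.** Section 13.4 sizes the trial on ventilator-free days (VFDs) over 28 days with a between-patient SD of 11.380: "100 patients per group will provide 90% power to detect an underlying true difference in means". The difference meant is 4.2 days for one dose against placebo, tested at 10% one-sided. The next paragraph defends the test level: "a 10% one-sided significance level is considered appropriate as this implies a 1 in 10 chance of a false positive finding". It adds that this suits the Phase II aim of finding a promising treatment. The synopsis carries the same text.

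Section 13.1 sets the comparisons for every formally analysed endpoint: "AZD9773 dose 1 versus placebo, AZD9773 dose 2 versus placebo, and combined AZD9773 dose arms 1 and 2 versus placebo". It then states: "Although there are three primary comparisons, this is an exploratory Phase IIb study and consequently no adjustment for multiple comparisons will be made". On the level it says: "The nominal significance level used for this study will be 10% one-sided".

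Section 6.2.1 gives the allocation; the system will "allocate patients to treatment groups (AZD9773: dose 1, dose 2, placebo) in a 1:1:1 ratio".

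Section 4.2 gives the purpose of having two active arms: both regimens "will be evaluated to determine which dose regimen should be employed in further clinical studies". Section 13.3.4 repeats the same three placebo comparisons for VFDs, each with an LSMean difference, 80% and 95% confidence intervals, and one-sided and two-sided p-values.

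**The concern.** The justification in Section 13.4 is tied to an aim at the level of the whole trial, namely whether the drug is promising. A reader will therefore take 1 in 10 as the chance that this trial wrongly points to an inactive drug. The protocol has three primary comparisons and ranks none above the others, so a positive result on any one of them is open to being read as a positive trial. On that reading the stated rate is too low. The protocol gives no other figure for the trial as a whole, and neither Section 13.4 nor the synopsis limits the figure to one comparison.

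A smaller, related gap concerns the choice of regimen. Section 4.2 makes that choice a purpose of the trial, but no listed comparison estimates the difference between the two doses. Without its interval, readers cannot see from the planned output how weakly or strongly the trial separates them.

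**Working it through.** **Inputs.** SD 11.380, 100 patients per group, difference 4.2 days, 10% one-sided, 90% power (Section 13.4). Three comparisons, unadjusted, each at nominal 10% one-sided (Section 13.1). Allocation 1:1:1 (Section 6.2.1).

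**1. The plan's own power figure.**
- SE of one dose versus placebo = 11.380 × √(2/100) = 1.609 days.
- Power = Φ(4.2/1.609 − 1.2816) = Φ(2.610 − 1.2816) = 0.908 (0.907 with the noncentral t).
- 97 per group would give 90%.

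The stated 90% is reproduced. A two-sided 10% test would give 83.3%, so the one-sided reading is the one the plan used.

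**2. Correlation of the three tests when the drug is inactive.** Let Z1 and Z2 be the test statistics for dose 1 and dose 2 versus placebo, and Z3 the one for the pooled doses.
- Z1 and Z2 share the placebo arm, and the arms are equal, so corr(Z1, Z2) = 0.5.
- Z3 = (Z1 + Z2)/√3, so corr(Z1, Z3) = corr(Z2, Z3) = 1.5/√3 = 0.866.

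**3. Chance of at least one false positive.** Each test is positive when Z > 1.2816.

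| Comparisons counted | Chance of at least one positive |
|---|---|
| Any single one | 10.0% |
| Two single doses: 0.10 + 0.10 − P(both) = 0.20 − 0.0324 | 16.8% |
| All three (numerical integration 0.1719; 8 million simulated draws 0.1718) | 17.2% |

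The pooled test adds only about 0.4 percentage points, because it is nearly determined by the other two. Treating the tests as independent would give 1 − 0.9³ = 27.1%, and adding the levels would give 30%. Neither applies to tests this strongly correlated.

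**4. Size relative to the stated rate.** 17.2/10 = 1.72, so the rate for the three comparisons together is about 72% higher than 1 in 10. 1/0.172 = 5.8, or about 1 in 6.

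**5. Precision of dose 2 minus dose 1.** With 100 per arm and SD 11.380 the SE is again 1.609 days.
- 80% CI half-width = 1.2816 × 1.609 = 2.06 days.
- 95% CI half-width = 1.96 × 1.609 = 3.15 days.

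Covariate adjustment may narrow these; the protocol gives no figure for by how much.

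**The case against.** The best defence is that there is no arithmetic error. A 10% one-sided level does mean 1 in 10 for each test, and the sentence follows directly on a power calculation for one dose against placebo. Section 13.1 declares the three comparisons openly, calls the level nominal and says why nothing is adjusted. Two-sided 95% intervals and p-values are reported alongside, so a reader can apply a stricter standard. All of this stands, and it is why the point concerns wording and not the design.

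It does not remove the point. The justification paragraph is not itself limited to one comparison, and it appeals to a trial-level aim. Waiving control across comparisons is legitimate; leaving 1 in 10 as the only stated rate invites a reading that the unadjusted design does not meet.

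Two stronger readings are tempting, and the protocol supports neither.

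- A reader might infer that the decision to continue development carries a 17% error rate. The protocol contains no rule that any one positive test triggers that decision.
- A reader might infer that the dose will be picked by setting two p-values side by side. Nothing says so. The protocol plans LSMean differences with intervals for each dose, exposure–response work (Sections 7.7.2 and 12.4), and safety and mortality by arm.

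On the missing contrast, it is fair to reply that its point estimate follows by subtracting the two placebo-referenced differences. Its interval, however, is not among the listed outputs.

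**Conclusion.** The concern holds as a matter of wording. The 1-in-10 statement is correct per comparison and incorrect as a rate for the set of primary comparisons, where it is 17.2% (about 1 in 6). Almost all of the excess comes from testing two doses.

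The figure assumes equal arms, approximately normal test statistics, no effect at either dose, a single analysis set, and that any one positive comparison counts as a finding. The protocol also plans per-protocol and intention-to-treat analyses, and models with and without covariates. Treating those as further chances of success would raise the rate by an amount that cannot be computed from the document.

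No analysis, estimate or sample size is wrong. The missing dose 2 versus dose 1 contrast is secondary: a useful addition in view of the aim in Section 4.2. Overall severity is moderate to minor.

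**What to change.** 1. In Section 13.4 and the synopsis, replace the unqualified rate with wording such as: *a 1 in 10 chance of a false positive finding per comparison, and about 17% for at least one of the three primary comparisons if neither dose has an effect*.
2. In Section 13.3.4, add the dose 2 minus dose 1 LSMean difference for VFDs with 80% and 95% confidence intervals, taken from the same covariance model and labelled as an estimate to inform the choice of regimen.

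No multiplicity adjustment is required. For information, holding 10% over all three would need about 5.5% one-sided per comparison, which lowers power per dose to about 84%. Nor is a single pooled primary test required. If only one dose gave 4.2 days, the pooled difference would be 2.1 days with SE 11.380 × √(1/200 + 1/100) = 1.394, and power Φ(2.1/1.394 − 1.2816) = 59%. That is a poor trade for a trial meant to compare two regimens with placebo.

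The cost is a sentence in two places and one contrast from a model already planned. There is no new data collection and no change in sample size. The only price is stating a less favourable error rate.

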13.5 Interim analyses

No formal interim analyses are planned.

13.6 Data monitoring committee

An IDMC will be established comprising three independent experts. The committee will meet at planned times (at a minimum once 100 patients have reached Day 29) to review the safety data from the study. Following their meeting, the IDMC will report to the sponsor and may recommend changes in the conduct of the study.

The IDMC will meet in open session with the study sponsor, followed by a closed meeting attended only by IDMC members. In the presence of any serious toxicity, the IDMC will consider recommending changes to the study or stopping the study. The final decision to modify or stop the study will sit with the sponsor.

The sponsor or IDMC may call additional meetings if at any time there is concern about the safety of the study.

Futility analysis will not be a responsibility of the IDMC.

Full details of the IDMC procedures and processes can be found in the IDMC Charter.

Appendix Date [REDACTED]

Appendix B
Additional Safety Information

THIS IS A PRINTED COPY OF AN ELECTRONIC DOCUMENT. PLEASE CHECK ITS VALIDITY BEFORE USE.

FURTHER GUIDANCE ON THE DEFINITION OF A SERIOUS ADVERSE EVENT (SAE)

Life threatening

‘Life-threatening’ means that the subject was at immediate risk of death from the adverse event (AE) as it occurred or it is suspected that use or continued use of the product would result in the subject’s death. ‘Life-threatening’ does not mean that had an AE occurred in a more severe form it might have caused death (eg, hepatitis that resolved without hepatic failure).

Hospitalisation

Out-patient treatment in an emergency room is not in itself a serious AE, although the reasons for it may be (eg, bronchospasm, laryngeal oedema). Hospital admissions and/or surgical operations planned before or during a study are not considered AEs if the illness or disease existed before the subject was enrolled in the study, provided that it did not deteriorate in an unexpected way during the study.

Important medical event or medical intervention

Medical and scientific judgement should be exercised in deciding whether a case is serious in situations where important medical events may not be immediately life-threatening or result in death, hospitalisation, disability or incapacity but may jeopardize the subject or may require medical intervention to prevent one or more outcomes listed in the definition of serious. These should usually be considered as serious.

Simply stopping the suspect drug does not mean that it is an important medical event; medical judgement must be used.

Examples of such events are:

- Angioedema not severe enough to require intubation but requiring iv hydrocortisone treatment
- Hepatotoxicity caused by paracetamol (acetaminophen) overdose requiring treatment with N-acetylcysteine
- Intensive treatment in an emergency room or at home for allergic bronchospasm
- Blood dyscrasias (eg, neutropenia or anaemia requiring blood transfusion, etc) or convulsions that do not result in hospitalisation
- Development of drug dependency or drug abuse

A GUIDE TO INTERPRETING THE CAUSALITY QUESTION

The following factors should be considered when deciding if there is a “reasonable possibility” that an AE may have been caused by the drug.

- Time Course. Exposure to suspect drug. Has the subject actually received the suspect drug? Did the AE occur in a reasonable temporal relationship to the administration of the suspect drug?
- Consistency with known drug profile. Was the AE consistent with the previous knowledge of the suspect drug (pharmacology and toxicology) or drugs of the same pharmacological class? OR could the AE be anticipated from its pharmacological properties?
- Dechallenge experience. Did the AE resolve or improve on stopping or reducing the dose of the suspect drug?
- No alternative cause. The AE cannot be reasonably explained by another aetiology such as the underlying disease, other drugs, other host or environmental factors.
- Rechallenge experience. Did the AE reoccur if the suspected drug was reintroduced after having been stopped? AstraZeneca would not normally recommend or support a rechallenge.
- Laboratory tests. A specific laboratory investigation (if performed) has confirmed the relationship?

A “reasonable possibility” could be considered to exist for an AE where one or more of these factors exist.

In contrast, there would not be a “reasonable possibility” of causality if none of the above criteria apply or where there is evidence of exposure and a reasonable time course but any dechallenge (if performed) is negative or ambiguous or there is another more likely cause of the AE.

In difficult cases, other factors could be considered such as:

- Is this a recognised feature of overdose of the drug?
- Is there a known mechanism?

Ambiguous cases should be considered as being a “reasonable possibility” of a causal relationship unless further evidence becomes available to refute this. Causal relationship in cases where the disease under study has deteriorated due to lack of effect should be classified as no reasonable possibility.

Clinical Study Protocol Appendix C

Drug Substance	AZD9773
Study Code	D0620C00003
Edition Number	1
Date	[REDACTED]

**Appendix C
IATA 6.2 Guidance Document**

THIS IS A PRINTED COPY OF AN ELECTRONIC DOCUMENT. PLEASE CHECK ITS VALIDITY BEFORE USE.

LABELLING AND SHIPMENT OF BIOHAZARD SAMPLES

International Airline Transportation Association (IATA) classifies biohazardous agents into 3 categories (http://www.iata.org/whatwedo/cargo/dangerous_goods/infectious_substances.htm). For transport purposes the classification of infectious substances according to risk groups was removed from the Dangerous Goods Regulations (DGR) in the 46th edition (2005). Infectious substances are now classified either as Category A, Category B or Exempt. There is no direct relationship between Risk Groups and categories A and B.

Category A Infectious Substances are infectious substances in a form that, when exposure to it occurs, is capable of causing permanent disability, life-threatening or fatal disease in otherwise healthy humans or animals. Cat A pathogens are eg. Ebola, Lassa fever virus

- are to be packed and shipped in accordance with IATA Instruction 602

Category B Infectious Substances are infectious Substances that do not meet the criteria for inclusion in Category A. Cat B pathogens are eg. Hepatitis A, B, C, D, and E viruses, Human immunodeficiency virus (HIV) types 1 and 2. They are assigned the following UN number and proper shipping name:

- UN 3373 – Biological Substance, Category B
- are to be packed in accordance with UN3373 and IATA 650

Exempt - all other materials with minimal risk of containing pathogens

- Clinical trial samples will fall into Cat B or exempt under IATA regulations.
- Clinical trial samples will routinely be packed and transported at ambient temperature in IATA 650 compliant packaging (http://www.iata.org/whatwedo/cargo/dangerous_goods/infectious_substances.htm).
- **Biological samples transported in dry ice require additional dangerous goods specification for the dry-ice content.**
- IATA compliant courier and packaging materials should be used for packing and transportation and packing should be done by an IATA certified person, as applicable.

- Samples routinely transported by road or rail are subject to local regulations which require that they are also packed and transported in a safe and appropriate way to contain any risk of infection or contamination by using approved couriers and packaging / containment materials at all times. The IATA 650 biological sample containment standards are encouraged wherever possible when road or rail transport is used.

THIS IS A PRINTED COPY OF AN ELECTRONIC DOCUMENT. PLEASE CHECK ITS VALIDITY BEFORE USE.

Clinical Study Protocol: Appendix D

Drug Substance	AZD9773
